### 3.3. Sample Size Consideration

The sample size for the Endurant Evo global program is calculated for both the primary safety endpoint and the primary effectiveness endpoint.

It is expected that the Endurant Evo AAA stent graft system will result in a MAE rate at 10% with respect to the primary safety endpoint and 90.5% treatment success for the primary effectiveness endpoint according to its predicates' performances shown in Table 1.

In order to pass both hypothesis tests with an overall study power of 80%, a sample size of 119 evaluable subjects will be required to pass each hypothesis with 90% statistical power (target significance level is 0.025.) To account for attrition of 15% (85% imaging compliance) at 12 months, 140 subjects will be enrolled globally to ensure at least 119 evaluable subjects. Note that a minimum of 50 subjects will be enrolled with the high neck angulation indication and a minimum of 70 subjects will be enrolled with percutaneous access. If a minimum of 50 high angle indication subjects are not enrolled as part of the first 140 subject cohort, Medtronic will continue enrollment for the high angulation indication but submit the PMA application to obtain approval for the 60° angulation indication with the 140 subject cohort data.

Table 1: Clinical Data from Talent AAA eLPS and Endurant Studies

Predicates	MAE within 30 Days	Successful Aneurysm Treatment at 12 Months
Talent AAA eLPS Arm	11% (18/166)	86% (107/125)
Endurant IDE Bifurcated Arm	4% (6/150)	95% (115/121)
Endurant IDE AUI Arm	11% (5/44)	97% (35/36)

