### **8.4. Analysis of the Primary Endpoints**

#### *Statistical Hypothesis:*

The primary safety endpoint will be tested against a predetermined safety Performance Goal (PG) using the following statistical hypotheses:

$$H_0: p \geq 20\% \text{ vs. } H_1: p < 20\%$$

where  $p$  is the proportion of subjects experiencing a MAE within 30 days of the index procedure in the target population of subjects treated with the Endurant Evo AAA Stent graft system and 20% is the safety PG.

The primary effectiveness endpoint will be tested against a predetermined effectiveness PG using following statistical hypotheses:

$$H_0: q \leq 80\% \text{ vs. } H_1: q > 80\%$$

where  $q$  is the proportion of subjects who have a successful aneurysm treatment in the target population of subjects treated with the Endurant Evo AAA Stent graft system and 80% is the effectiveness PG.

If the null hypothesis ( $H_0$ ) is rejected at the one-sided 0.025 statistical significance level, it is considered that the PG for the associated endpoint has been reached.

Both safety and effectiveness endpoints are dichotomous study outcomes; hence, an exact method based on the binomial distribution will be used for the hypothesis testing.

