**Table 4: Imaging based Event Rate Calculation:**

Event rate = $m/n$	At 1 Month	At 6 Months	At 12 Months
$m = \text{No. of Subjects Who Had Event(s)}$	No. of subjects who had an event with scan day within the 1-month window.	No. of subjects who had an event with scan day within the 6-month window.	No. of subjects who had an event with scan day within the 12-month window.
$n = \text{No. of Subjects Who Had Readable Images}$	No. of subjects who had a readable image within the 1-month window.	No. of subjects who had a readable image within the 6-month window.	No. of subjects who had a readable image within the 12-month window.
Event rate = $m/n$	Through 1 Month	Through 6 Months	Through 12 Months
$m = \text{No. of Subjects Who Had Event(s)}$	No. of subjects who had an event with scan day within the 1-month window.	No. of subjects who had an event with scan day within 1- or 6-month windows.	No. of subjects who had an event with scan day within 1-, 6- or 12-month windows.
$n = \text{No. of Subjects Who Had Readable Images}$	No. of subjects who had a readable image within the 1-month window.	No. of subjects who had an event (counted in m) or had a readable image within the 6-month window.	No. of subjects who had an event (counted in m) or had a readable image within the 12-month window.

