## 8.5. Analysis of the Secondary Endpoints

Descriptive statistical analyses will be performed on secondary endpoints. No inferential statistical analysis is planned for secondary endpoints.

Event rates such as mortality, secondary procedures, serious adverse events, conversion to open surgery, and aneurysm ruptures will be calculated in the same way as the MAE rate, specified in Table 3.

The survival from all-cause and aneurysm-related mortality over one year time or longer will be presented with the Kaplan-Meier survival curve and the associated Kaplan-Meier estimate will be calculated along with its standard error using the Greenwood method.

Imaging based event rate such as stent graft migration, aneurysm expansion, endoleaks, stent graft occlusions, and device deficiencies will be calculated in the way as specified in Table 4.

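### SAP Table 4's 'through' denominators depend on the outcome, so occlusion and device-deficiency rates read modestly high if images are missing independently of outcome

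*SAP*

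**What the plan says.** SAP 8.4, Table 4, defines two kinds of imaging rate. The *at* rates divide subjects with an event in a window by subjects with a readable image in that window. The *through* rates accumulate events over windows: for 12 months the numerator takes events from the 1-, 6- or 12-month window, and the denominator is "No. of subjects who had an event (counted in m) or had a readable image within the 12-month window". The 6-month column has the same form.

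SAP 8.5 says that "stent graft occlusions, and device deficiencies will be calculated in the way as specified in Table 4", and SAP section 5 defines both as *through* endpoints. Occlusion through 12 months is also a component of the primary effectiveness composite. SAP 8.4 says that the composite's imaging components come from core lab reads. Neither document states the composite's denominator.

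SAP 3.3 plans for 15% attrition at 12 months and states that "a sample size of 119 evaluable subjects will be required to pass each hypothesis with 90% statistical power". SAP 8.3 rules out imputing outcomes and makes a tipping-point analysis optional.

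**The concern.** Take two subjects with readable images at 1 and 6 months and none at 12 months. If one had an occlusion at 6 months, that subject enters numerator and denominator. The other, clean at both visits, enters neither. The denominator row is labelled as subjects with readable images, but the second subject's readable images do not count. Event-free follow-up that was observed is discarded, and only for subjects without an event.

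The endpoints matter. Device deficiencies include the stent and anchoring-pin fractures that Protocol L.2 defines. Protocol C.5 gives stent fractures and detachment as the reason enrollment ended, and Protocol J.3 compares the device's risks with those of commercially available devices. A rate used in such a comparison should not carry an avoidable bias. If the same rule were used for the primary composite, it could also lower the observed success rate.

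**Working it through.** **The plan's own figure.** Inputs from SAP 3.3 and 8.4: "80% is the effectiveness PG"; "90.5% treatment success for the primary effectiveness endpoint"; the null hypothesis is "rejected at the one-sided 0.025 statistical significance level"; "an exact method based on the binomial distribution will be used for the hypothesis testing". With 119 evaluable subjects the exact test succeeds at 104 or more successes, with actual type I error 0.0241 and power 90.1% at a true 90.5%. Also 119/0.85 = 140. The stated sample size reproduces.

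**Bias in a *through* rate.** Let e be the probability of an event seen before the last window, l the probability of a first event in the last window, and r the probability of a readable last image, independent of outcome. Assume earlier images are complete.

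- Expected numerator: e + l·r.
- Expected denominator: e + (1 − e)·r.
- Excess over the true rate e + l: e(1 − r)(1 − e − l) / [e + (1 − e)r].

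The excess is positive whenever e > 0 and r < 1. The relative excess is largest when all events are early, where the ratio of reported to true rate is 1/[e + (1 − e)r]. This is below 1/r = 1/0.85 = 1.176, so the excess is at most about 18%.

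At r = 0.85 (the true rates and the early share are assumptions; the documents give neither):

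- True 5%, half early: (0.025 + 0.025×0.85)/(0.025 + 0.975×0.85) = 0.04625/0.85375 = 5.4%.
- True 5%, all early: 0.05/(0.05 + 0.95×0.85) = 0.05/0.8575 = 5.8%.
- True 10%, half early: 0.0925/0.8575 = 10.8%.
- True 10%, all early: 0.10/0.865 = 11.6%.

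As a further pattern, assume 8% lost after 1 month, another 7% after 6 months, and events spread evenly over the three windows. A true rate p then reads 0.9233p/[0.9233p + 0.85(1 − p)]: 5.4%, 10.8% and 21.4% for 5%, 10% and 20%. In simulated data of this kind, with no competing events, a life-table estimate gave 5.0%, 10.0% and 20.0%.

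**When the bias reverses.** The true rate is a weighted average of the Table 4 rate (subjects counted) and the unseen late-event risk of those dropped. Table 4 therefore reads high only while that risk is below the Table 4 rate itself. In the half-early 5% case, retained subjects free of early events have a late risk of 0.025/0.975 = 2.6%. The dropped subjects would need more than 5.4%, about twice that, for the bias to change sign.

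**The composite, only if the rule is carried into it.** Let f be the share of failures known before 12 months (not in the documents). Each of 140 subjects is a counted failure with probability 0.095[f + 0.85(1 − f)], a counted success with probability 0.905×0.85, or dropped. This treats 90.5% as the true rate in all subjects. Type I error is computed at a true full-cohort rate of 80%.

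| f | Expected observed success | Power, evaluable number varying | Power at fixed n | Type I error, n varying |
|---|---|---|---|---|
| 0 (no effect of the rule) | 90.5% | 87.7% | 90.1% (n = 119) | 0.0188 |
| 0.25 | 90.1% | 84.7% | 87.3% (n = 119) | 0.0120 |
| 0.5 | 89.7% | 81.4% | 83.3% (n = 120) | 0.0075 |

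**The case against.** A reader might infer that effectiveness power is below the stated 90%. The documents do not support this as a fact, for four reasons.

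- Table 4 governs imaging event rates. Using it for the composite is an inference, since no composite denominator is given.
- The 90.5% is attributed to the predicates and equals the mean of 86% and 95%. Those 12-month rates rest on 125 and 121 subjects, against 166 and 150 for 30-day MAE, and the footnote to SAP Table 1 says that they counted every occlusion over the period. The planning rate may already carry the same kind of counting, in which case power stays near 90%. This is suggestive, not proven.
- The early share is unknown. Diameter increase is judged only at 12 months, and Type I/III endoleak mainly so. Technical failure, rupture and conversion can be known early, but they are not Table 4 imaging rates.
- With no Table 4 effect at all, power is 87.7% once the evaluable number varies around 119. That part of any gap from 90% has another cause.

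It can also be said that the affected secondary rates are descriptive and that the bias is small beside sampling error: at 5% and n = 119 the standard error is √(0.05×0.95/119) = 2.0 points, against a bias of 0.4 to 0.8. Both statements stand. They limit the importance of the point, but the estimate remains avoidably biased.

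Finally, a life-table estimate also assumes non-informative missing images, and one minus Kaplan-Meier overstates incidence if death or conversion is simply censored. This stands too, and the fix has to allow for it.

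**Conclusion.** The outcome-dependent denominator is in the text of Table 4, and SAP 8.5 applies it to occlusions and device deficiencies. If missing images are unrelated to outcome, the *through* rates are overstated, by at most about 18% in relative terms at 15% attrition and by roughly 8% when half the events are early. The direction is not assured: higher risk among the dropped subjects could shrink or reverse it. The 15% is itself a planning assumption.

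An effect on power is conditional. Power falls to about 85% with a quarter of failures known early, or 81% with half, only if the Table 4 rule is used for the composite and 90.5% is a true full-cohort rate; the comparison is 87.7% without the rule. Even then the error is conservative. It lowers the chance of declaring success and does not favour a false success. This is a minor point, worth correcting because the correction is cheap.

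**What to change.** In SAP 8.4 and 8.5, for imaging events counted through 6 and 12 months:

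1. Report as the main estimate a cumulative incidence by imaging window (life-table form) that uses every readable image, censors at the last readable image, and handles death and conversion as competing events. State that it assumes non-informative missing images.
2. Show the Table 4 ratio beside it, so that comparison with the predicates' simple proportions is kept.
3. State the denominator of the primary effectiveness composite, including how a subject with no early failure and no readable 12-month image is counted, and give the power that applies under that denominator.

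The cost is a few lines of SAP wording and one standard procedure; the SAP already plans Kaplan-Meier estimates with Greenwood errors for mortality. No new data are needed. The drawback is that the main estimate no longer has the form of the predicate rates, which is why both should appear. Enrollment closed at 139, so restating power serves interpretation only and cannot change the sample size.

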## 8.5. Analysis of the Secondary Endpoints

Descriptive statistical analyses will be performed on secondary endpoints. No inferential statistical analysis is planned for secondary endpoints.

Event rates such as mortality, secondary procedures, serious adverse events, conversion to open surgery, and aneurysm ruptures will be calculated in the same way as the MAE rate, specified in Table 3.

The survival from all-cause and aneurysm-related mortality over one year time or longer will be presented with the Kaplan-Meier survival curve and the associated Kaplan-Meier estimate will be calculated along with its standard error using the Greenwood method.

Imaging based event rate such as stent graft migration, aneurysm expansion, endoleaks, stent graft occlusions, and device deficiencies will be calculated in the way as specified in Table 4.

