### H.1 Analysis of Clinical Data

All observations will be analyzed descriptively. In general, qualitative parameters will be described by their distribution frequencies; quantitative parameters will be described by their mean, standard deviation, minimum, maximum, median, and number of subjects with assessable data.

The survival from all-cause mortality over one year time or longer will be described by the Kaplan-Meier survival curve and the associated Kaplan-Meier estimate will be calculated along with its standard error using the Greenwood method.

For events such as AEs, deaths and secondary procedures, that can occur or are observed at any time during the study, no time window will be applied. For such events, an event that occurs "within 1 month or 30 days" is an event that takes place between Days 0 to 30, inclusive. Similarly, an event that occurs "within 12 months or 365 days" is an event occurring between Day 0 to Day 365, inclusive. Date of event onset will be used to determine when the event occurred. Day 0 is referring to the day of index procedure.

For image-based assessments, such as stent-graft endoleak, patency, and other observations, the following time windows will be applied for by-visit data summaries:

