**Long Term Follow-up:**

Subjects will be followed for a total of 5 years from index procedure.

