## L.2 Definitions

Major Adverse Events (MAEs)	Definition
All-Cause Mortality	Death from any cause.
Bowel Ischemia	Bloody diarrhea with confirmation via colonoscopy of ischemia or the operative or postmortem demonstration of ischemic changes in the large or small intestine and requires surgical intervention.
Myocardial Infarction	Evidenced on 2 of the 3 following conditions: new clinical symptoms suggesting MI, changes on ECG consistent with MI, and elevated CK > 2 times the upper normal limit (per the normal ranges of the institution).
Paraplegia	Complete loss of motor function in the lower extremities occurring intra- or postoperatively and persisting >1 month.
Procedural Blood Loss $\geq$ 1000 cc	A blood loss $\geq$ 1000 cc occurring before the subject leaves the operating room.
Renal Failure	Failure of renal function requiring dialysis.
Respiratory Failure	Need for mechanical ventilation for > 24 hours postoperatively, or re-intubation for any reason.
Stroke	Development of a new neurological deficit that persists > 24 hours, or worsening of previous neurological symptoms that persist > 24 hours and classified as stroke by a physician.

Secondary Endpoints:	Definition
Aneurysm-Related Mortality	
Aneurysm-related mortality is defined as death from rupture of the abdominal aortic aneurysm or from any initial or secondary procedure intended to treat the AAA. If a death occurred within 30 days of any procedures intended to treat the AAA, then it is presumed to be aneurysm-related unless there is evidence to the contrary. Deaths that occurred after 30 days of any procedures intended to treat the AAA that are procedure-related should be aneurysm-related.
 
Ultimate adjudication of relatedness of death will be made by the Clinical Events Committee (CEC). Excluded are aneurysms in anatomic areas other than the targeted segment treated by the Endurant Evo AAA stent graft system.

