## **1. Introduction**

This document outlines the detailed statistical methods to be implemented for the data collected within the scope of Endurant Evo US Clinical Trial. This document is designed for internal use as a guideline for study Biostatistician and Statistical Programmer(s). Study protocol is the primary resource if clarification is needed for the contents of this document. Analysis results obtained from the analyses outlined in this document will be the basis of the Clinical Study Report for this study.

As with any statistical analysis plan, the proposed methods and approaches to the data analysis should be viewed as flexible. Changes to the plan may arise if the emerging picture suggests that deviations from the original plan would provide a more reliable and valid analysis of the data. The purpose of this plan is to provide general, and in some instances, specific guidelines from which the analysis will proceed. Nonetheless, sound statistical reasoning must substantiate deviations from these guidelines.

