### **3.1. Treatment and Subject Enrollment**

The study population will include those subjects who are appropriate candidates for endovascular repair of infrarenal abdominal aortic or aortoiliac aneurysms, and who meet the Inclusion/Exclusion criteria (defined in the Clinical Investigation Plan Section D).

For subjects that are treated with the bifurcated stent graft minimal 3 pieces will be implanted in the target segment; one bifurcated stent graft component and 2 limb stent graft components. For subjects that are treated with the Aorto-Uni-Iliac (AUI) component approximately 2 pieces will be implanted in the target segment; the AUI stent graft component and one limb stent component. Additional stent graft extensions might be needed to cover the complete target lesion length.

Globally, a total of 140 subjects will be concurrently enrolled in the United States and outside the United States to support the primary endpoints. Up to 50% of subject data used to support PMA approval may come from subjects enrolled at sites outside of the US under a separate CE Mark study protocol; called the Endurant Evo International Clinical Trial protocol.

The Endurant Evo International Clinical Trial protocol and Endurant Evo US Clinical Trial protocol will be identical with respect to the inclusion/exclusion criteria, and follow up data collection.

Subjects will have required follow-up evaluations at the following time points:

- 1 month following the index procedure
- 6 months following the index procedure
- 12 months following the index procedure

Subjects will be followed until the last subject enrolled has completed the 1 year follow-up visit or until PMA approval is obtained in the US (whatever is later), however, Medtronic will work with FDA to determine if longer term follow after PMA approval is required.

The Endurant Evo Global Clinical program will be conducted at up to 30 sites worldwide with up to 20 sites participating under the Endurant Evo US Clinical trial protocol in the United States and with approximately 10 sites participating under the Endurant Evo International Clinical trial protocol outside the United States. In the United States, a minimum of 70 subjects will be enrolled at up to 20 investigational sites. Investigators at any single site may not enroll more than 20% of the total global enrollment (140 subjects) in the trial.

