**Table 2: Time Windows for Statistical Analyses**

Study Visit	Target Day	Time Window
Implant	Day 0	Day 0
1 Month	Day 30	1 – 90 days
6 Months	Day 183	91 – 304 days
12 Months	Day 365	305 – 548 days
In case long term follow up data will be collected, the following time windows will apply.		
2 Year	Day 731	549 – 913 days
3 Year	Day 1096	914 – 1278 days
4 Year	Day 1461	1279 – 1644 days
5 Year	Day 1826	1645 – 2009 days

If different type of images are used but have different finding in the same time window, the imaging technique and sensitivity matrix (Appendix 12.1) will be applied. Finding from higher visibility image will be used for analysis. If there are two or more assessments from the same type of image in the same time window, then the assessment closest to the target day will be used in the analysis of event rate at a given time point.

Statistical analyses for this study will be performed using the Statistical Analysis System (SAS) for Windows (Version 9.1 or higher) or other widely-accepted statistical or graphical software.

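### Beyond one year, the Kaplan-Meier estimate of aneurysm-related mortality in SAP 8.5 is a net quantity whose complement overstates actual risk; a cumulative incidence estimate should be reported instead

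*SAP*

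**What the plan says.** SAP 8.5 plans one method for two mortality outcomes: "The survival from all-cause and aneurysm-related mortality over one year time or longer will be presented with the Kaplan-Meier survival curve". The estimate is to be "calculated along with its standard error using the Greenwood method". Protocol H.1 is narrower and plans this method for all-cause mortality only: "The survival from all-cause mortality over one year time or longer will be described by the Kaplan-Meier survival curve". The SAP alone extends it to aneurysm-related mortality.

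Protocol L.2 defines aneurysm-related mortality as "death from rupture of the abdominal aortic aneurysm or from any initial or secondary procedure" intended to treat the aneurysm, with relatedness finally adjudicated by the Clinical Event Committee. Death from an unrelated cause therefore rules out the event.

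The two documents differ on horizon. Protocol H.1 says "Subjects will be followed for a total of 5 years from index procedure". SAP 3.1 sets a shorter minimum, "Subjects will be followed until the last subject enrolled has completed the 1 year follow-up visit or until PMA approval is obtained in the US" (whichever is later), and SAP Table 2 treats later data as conditional: "In case long term follow up data will be collected, the following time windows will apply". The SAP introduction defers to the protocol: "Study protocol is the primary resource if clarification is needed for the contents of this document".

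The named secondary endpoint, aneurysm-related mortality within 30, 183 and 365 days, does not use Kaplan-Meier. SAP 8.5 sends mortality rates at those times to the crude proportion in Table 3. Secondary endpoints are descriptive only. Neither document mentions competing risks or cumulative incidence, or says how deaths from other causes enter the aneurysm-related curve.

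**The concern.** Kaplan-Meier suits all-cause mortality, where no other event can pre-empt the outcome. For aneurysm-related death, a subject who dies of something else can no longer have the event. Standard practice censors that subject, removing them from the risk set. The estimator then assumes that, had they lived, they would have had the same later aneurysm-related hazard as those who remain. The resulting 1 − KM answers a hypothetical question: how many would die of the aneurysm or its treatment if nobody died of anything else. It is larger than the proportion who do die that way.

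Enrollment was terminated after unanticipated device effects, and remaining follow-up concentrates on events possibly related to aneurysm, device or procedure (Protocol F.6 and J.3). Long-term aneurysm-related death is thus a figure that readers will look for. Shown beside an all-cause curve, it would naturally be read as actual risk, and it would be too high. The two causes would also not add up: cause-specific 1 − KM values do not sum to all-cause 1 − KM.

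**Working it through.** **Plan's own figure.** There is none to reproduce: neither document gives an aneurysm-related or other-cause mortality rate. The sizes below rest on assumed inputs, shown as a range.

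**Direction.** Both estimators use the same ratio of deaths to subjects at risk at each aneurysm-related death. Kaplan-Meier weights it by survival from aneurysm-related death alone; Aalen-Johansen weights it by survival from all causes. Once an other-cause death precedes an aneurysm-related one, the first weight is larger. So 1 − KM exceeds the cumulative incidence whatever the shape of the hazards.

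**Formulas.** With constant, independent hazards h1 (aneurysm-related) and h2 (other causes), at time t in years:

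- 1 − KM = 1 − exp(−h1·t)
- cumulative incidence (CIF) = h1/(h1 + h2) × [1 − exp(−(h1 + h2)·t)]

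**Assumed inputs.** Other-cause mortality at 5 years, as 1 − exp(−5·h2), from 10% to 50%; 5-year 1 − KM mainly from 1% to 5%.

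**Worked case.** Other-cause mortality 30%, 1 − KM 2%: h1 = −ln(0.98)/5 = 0.00404 and h2 = −ln(0.70)/5 = 0.07133. CIF = 0.00404/0.07537 × (1 − 0.98 × 0.70) = 0.0536 × 0.314 = 1.68%. Ratio 2/1.68 = 1.19.

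**Results at 5 years, constant hazards:**

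| Other-cause mortality | CIF when 1 − KM = 2% | Ratio | CIF when 1 − KM = 5% | Gap (points) |
|---|---|---|---|---|
| 10% | 1.90% | 1.05 | 4.75% | 0.25 |
| 20% | 1.79% | 1.12 | 4.49% | 0.51 |
| 30% | 1.68% | 1.19 | 4.21% | 0.79 |
| 40% | 1.57% | 1.28 | 3.92% | 1.08 |
| 50% | 1.44% | 1.38 | 3.62% | 1.38 |

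For 1 − KM of 1% to 5%, the gap runs from 0.05 points (1%, other-cause mortality 10%) to 1.38 points (5%, other-cause mortality 50%), and the relative overstatement from about 5% to about 39%.

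**The same set as yearly hazards.** Aneurysm-related 1% and other-cause 6% a year: 4.88% against 4.22%. At 1% and 8%: 4.88% against 4.03%. At 0.5% and 5%: 2.47% against 2.19%.

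**At 1 year.** The ratio is 1.01 to 1.07. The gap is at most 0.14 points, even where 5-year 1 − KM is 10%.

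**Hazard shape.**

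- All aneurysm-related hazard in days 0 to 30, 1 − KM 2%: ratio 1.001 to 1.006.
- All of it in years 3 to 5: CIF = exp(−2·h2) × h1/(h1 + h2) × [1 − exp(−3(h1 + h2))], with h1 = −ln(1 − KM)/3. The ratio is about 1.08, 1.28 and 1.61 at other-cause mortality of 10%, 30% and 50%.

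**Scale.** Global enrollment was 139 (Protocol C.5), so one subject is 1/139 = 0.7 points. At a 5% risk, the standard error without censoring is √(0.05 × 0.95/139) = 1.8 points.

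**The case against.** The case for leaving the plan alone is fair in several respects. The SAP promises a survival curve for aneurysm-related mortality and does not say that its complement will be presented as the proportion who die. Under independent censoring the curve has a legitimate net interpretation, so this is partly a choice of estimand. The named time points use Table 3, nothing inferential depends on the curve, and any overstatement runs against the device, so it cannot hide a safety signal. At 139 subjects the gap is within sampling error in most scenarios. Protocol L.2 presumes deaths within 30 days of an aneurysm procedure to be related unless there is contrary evidence, so early clustering, with almost no gap, is plausible. All of this stands, and it makes the point minor. It does not remove it: the SAP does not label the curve as a net quantity, and sampling error does not excuse a bias of known direction that is cheap to avoid.

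A reader might infer more than the documents support:

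- That the plan expressly censors other deaths. No censoring rule is written. It is what standard Kaplan-Meier for this event implies; counting other deaths as events would only reproduce the all-cause curve.
- That other-cause death is shown to be substantial. No rate is given. Support is indirect: Protocol B.1 describes an elderly, comorbid population, L.7 reports that 84.5% of claims with a principal AAA diagnosis are age 65 or older, and D.2 excludes only a life expectancy of 1 year or less.
- That Kaplan-Meier keeps dead subjects in the risk set, or that Greenwood is the wrong variance. Neither is so. Censored subjects leave the risk set, and Greenwood is the right variance for the Kaplan-Meier quantity. The difficulty is what that quantity means.
- That the SAP itself commits to 5-year reporting. The 5-year horizon is the protocol's; the SAP says one year or longer and treats later data as conditional.

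**Conclusion.** The point holds as a low-priority improvement to long-term descriptive reporting. The direction is certain once other-cause deaths precede aneurysm-related ones. The size is conditional: about 5% to 39% relative at 5 years, 0.05 to 1.4 points when 1 − KM is 1% to 5%, assuming other-cause mortality of 10% to 50% and constant, independent hazards. Early clustering takes it to almost nothing; late occurrence, which cannot be ruled out for a device followed for stent fracture, makes it larger. At 1 year it is negligible. Neither primary test and none of the 30-, 183- and 365-day rates depends on it; whether the Table 3 rule is itself sound is a separate question.

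**What to change.** In SAP 8.5, split the sentence on survival curves:

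- All-cause mortality: keep Kaplan-Meier with the Greenwood standard error.
- Aneurysm-related mortality beyond 1 year: report the Aalen-Johansen cumulative incidence with its own variance, treating non-aneurysm death as a competing event, and state how subjects who die of other causes are handled.
- Optionally, keep the cause-specific Kaplan-Meier curve as a secondary display for comparison with earlier devices, labelled as a net quantity with other-cause deaths censored.

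No new data are needed. The Clinical Event Committee reviews all deaths (Protocol F.6.5) and adjudicates their relatedness (L.2), and adverse events leading to death remain reportable in years 3 to 5 (F.6). The cost is a short SAP edit, slightly more analysis work, and a main estimate less directly comparable with earlier Kaplan-Meier reports, which the secondary display would offset.
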